Post-study survey. At the end of the study, before debriefing and being informed of the condition they were assigned to, participants answered a few questions about their experience of the stimulation and the tVNS device. Specifically, we asked about **awareness of the stimulation** ("How much, if at all, could you feel the tingling sensation during the conversations?"), **general discomfort** ("How uncomfortable was wearing the tVNS device [i.e., the clip you had on your ear] throughout the study?"), **perceived influence of discomfort on interactions** ("How much, if at all, did the discomfort [from wearing the clip] affect your conversations?"), and **perceived influence of tVNS on interactions** ("How much, if at all, do you think the device changed the way you felt or interacted with your partner during the conversations?"). All items were rated on a 5-point scale.

Study Procedure

Interested participants first completed a screening questionnaire to confirm eligibility. Eligible participants were then contacted via email to schedule a lab visit. Two days prior to the scheduled visit, participating couples received a link to a consent form and a questionnaire assessing sociodemographic information and relationship characteristics. Couples were randomly assigned to either tVNS or sham stimulation condition when they both completed the pre-visit survey. Each couple had an equal chance of being in either group.

Upon arrival at the lab, partners were escorted to separate rooms where they each received a full overview of the study and underwent threshold testing for stimulation. Then partners reunited in the same room, were connected to physiological sensors, and spent five minutes, resting in a comfortable seated position (baseline). As shown in Figure 1, they were seated at an angle, partially facing each other, with their bodies slightly tilted toward the front where a fixed wall-mounted camera was positioned. Participants were recorded during gratitude and conflict interactions. Full study procedure, including the timing of the stimulation is illustrated in Figure 2. Following a cool-down period, participants completed a brief questionnaire about their experience with the stimulation and were debriefed. They also signed an additional consent form for the use of their recorded videos.

Figure 1. Example Positioning of the Couple During the Study

[figure not shown]

Figure 2. Overview of Study Procedure

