tVNS effects on physiological reactivity. As in previous research, we will calculate reactivity scores by subtracting the raw RSA score during the last 30 seconds of baseline from every segment of the interaction. We will fit a multilevel model, first estimating the effect of condition (coded as -0.5 for sham and 0.5 for tVNS) on RSA reactivity with no covariates. As in previously described multilevel models, we will include a random intercept for participants nested within couples, and as recommended for physiological data, with autoregressive covariance structure of the residuals. In our follow-up models, we will control for sex (male/female/other), age, BMI, and relationship duration, which can influence physiological reactivity to conflicts. Then, to rule out the possibility that any condition effects are reducible to differences in the experience of the stimulation, the next model will additionally control for stimulation intensity and discomfort reported at the end of the study. We will repeat these analyses using IBI in place of RSA.

References

- Algoe, S. B., Fredrickson, B. L., & Gable, S. L. (2013). The social functions of the emotion of gratitude via expression. *Emotion*, 13(4), 605–609.
- Arend, M. G., & Schäfer, T. (2019). Statistical power in two-level models: A tutorial based on Monte Carlo simulation. *Psychological Methods*, 24(1), 1-19.
- Caldwell, W., da Estrela, C., MacNeil, S., & Gouin, J. P. (2019). Association between romantic partners' rumination and couples' conflict is moderated by respiratory sinus arrhythmia. *Journal of Family Psychology*, 33(6), 640-648.
- Geiss, S. K., & O'Leary, K. D. (1981). Therapist ratings of frequency and severity of marital problems: Implications for research. *Journal of Marital and Family Therapy*, 7(4), 515-520.
- Godfrey, D. A., & Babcock, J. C. (2020). Facial affect recognition moderates the relation between autonomic nervous system reactivity and aggression during dyadic conflict. *Psychophysiology*, 57(9), e13588.

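### RSA and IBI are corrected for baseline only by subtracting one 30-second epoch; no model includes baseline as a covariate, which may cost precision

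*Combined protocol and SAP*

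**What the plan says.** Under Physiological data acquisition, ECG is recorded continuously through baseline and interactions, and RSA is scored in 30-second intervals. Under Study Procedure, baseline is five minutes of seated rest, which is ten such intervals.

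In the Statistical Analysis Plan, paragraph on physiological reactivity, "we will calculate reactivity scores by subtracting the raw RSA score during the last 30 seconds of baseline from every segment of the interaction". One interval in ten is therefore used. The first model estimates the condition effect "on RSA reactivity with no covariates". In the follow-up models "we will control for sex (male/female/other), age, BMI, and relationship duration", and then "the next model will additionally control for stimulation intensity and discomfort reported at the end of the study". The paragraph ends: "We will repeat these analyses using IBI in place of RSA". Baseline RSA or IBI is a covariate in none of these. The stated reason for the subtraction is consistency with earlier research.

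On the order of events, Study Procedure says: "Couples were randomly assigned to either tVNS or sham stimulation condition when they both completed the pre-visit survey". At the visit, in separate rooms, "they each received a full overview of the study and underwent threshold testing for stimulation"; the baseline rest came after that. The unheaded opening section names HRV level and reactivity as one of the primary outcome variables.

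**The concern.** A change score assumes that each unit of baseline carries over in full to the interaction. One 30-second epoch is a noisy measure of a person's resting level, so the slope that best predicts the interaction is often below 1. Subtracting the whole epoch then adds noise. That noise is the same in all of a participant's segments, so it does not average out over segments, and a participant random intercept or autoregressive residuals do not remove it. It sits in the between-person variance against which the couple-level condition effect is tested.

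The reasons given under Physiological data acquisition for 30-second epochs concern epoch length. They do not address the fixed slope or the use of one epoch. At stake is a wider interval and lower power on a named primary outcome variable than the recorded data might allow.

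**Working it through.** **The plan's own figure.** The opening section gives 70 dyads, a standardized Level-2 effect of .40, a Level-1 effect of .10, an intraclass coefficient of 0.5 and more than 82% power. With both variance components set to 1 and reduced by the effects, SE = sqrt((0.84 + 0.99/2)/70) = 0.138, and power = Phi(0.40/0.138 - 1.96) = 82.5% (noncentral t: 81.5%). The figure reproduces. It names no outcome, so I do not carry it over to reactivity.

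**Simple check.** If the baseline epoch and the interaction score have equal SDs and correlation rho, the variance with baseline as covariate, divided by the change-score variance, is (1 + rho)/2. For rho = .3, .5, .7, .9 this is 0.65, 0.75, 0.85, 0.95. Simulation with 70 dyads gave 0.661, 0.767, 0.864, 0.966. Comparing square roots, estimating the slope costs about 0.7 to 1.0 percentage point of SE.

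**Couple-level check.** All inputs here are assumptions; the documents supply only the epoch length and the durations.
- True baseline variance 1; true task variance V; correlation r; partner correlation 0.5 in the true levels.
- Epoch noise variance v = (1 - rel)/rel, where rel is single-epoch reliability; AR(1) with coefficient phi; independent between partners.
- 12 segments (the six-minute discussion). The variance of their mean noise is v times f, with f = (1/12)[1 + 2 x sum of (1 - k/12)phi^k] = 0.146 at phi 0.3 and 0.281 at phi 0.6.

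Per participant: last epoch L = 1 + v; task mean T = V + vf; covariance c = r sqrt(V); slope b = c/L. Adding the partner covariances: L* = L + 0.5, T* = T + 0.5V, c* = 1.5c. Then
- planned variance P = L* + T* - 2c*
- adjusted variance A = T* + b²L* - 2bc*

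Middle case (r 0.7, rel 0.7, phi 0.3, V 1): v = 0.429, L* = 1.929, T* = 1.563, c* = 1.05, b = 0.49. P = 1.929 + 1.563 - 2.10 = 1.391. A = 1.563 + 0.463 - 1.029 = 0.997. A/P = 0.716, and 1 - sqrt(0.716) = 15%. The single epoch's noise is 0.429/1.391 = 31% of P.

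| r / rel / phi | V | b | P | A | A/P | SE lower by |
|---|---|---|---|---|---|---|
| 0.7 / 0.7 / 0.3 | 0.8 | 0.438 | 1.313 | 0.810 | 0.617 | 21% |
| same | 1 | 0.490 | 1.391 | 0.997 | 0.716 | 15% |
| same | 1.25 | 0.548 | 1.518 | 1.230 | 0.810 | 10% |
| same | 2 | 0.693 | 2.021 | 1.931 | 0.955 | 2% |
| 0.9 / 0.95 / 0.6 | 1 | 0.855 | 0.3674 | 0.3413 | 0.929 | 4% |
| same | 1.25 | 0.956 | 0.4237 | 0.4229 | 0.998 | 0.1% |
| 0.95 / 0.98 / 0.6 | 1 | 0.931 | 0.1762 | 0.1702 | 0.966 | 2% |

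With V = 1, r and rel each 0.6-0.8, phi 0-0.3 and 12 or 22 segments, A/P runs from 0.613 to 0.809, so the SE is 22% to 10% lower. With the two high-reliability rows the range is about 2-22%. The gain shrinks as b approaches 1. At 0.1% it is smaller than the slope-estimation cost above, so it may be nil with 70 couples.

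**Five-minute mean.** Let participants settle at different rates during baseline, with settling SD equal to the true-level SD and fading to zero by the last epoch. The mean alone as covariate then gives variance ratios of 1.501 and 2.422 in the two high-reliability cases at V = 1, so the SE is 23% and 56% higher than planned. The last-epoch result is unchanged by such settling. Last epoch plus mean gives 0.620 in the middle case without settling (21% lower); at V = 1.25, 1.5 and 2 that gain falls to 16%, 13% and 9%. In that middle case almost all the weight goes to the mean (0.63, against 0.02 for the last epoch).

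**The case against.** The strongest reply is that this is a choice between valid estimators. The change score is stated in advance, follows a convention, and nothing in the documents contradicts it. That stands, and it limits the point to precision.

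Second, the gain depends on variances that the documents do not give. That also stands: in the table, raising task variance to 1.25 takes a 4% gain to 0.1%.

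Third, the last epoch is the one furthest from threshold testing at the assigned ear site. In the middle case, a carry-over that faded before the last epoch would leave the planned contrast untouched but move a model containing the five-minute mean by about 0.63 of the mean shift. This is a good reason not to make the mean a main covariate. It does not count against the last epoch, which a faded carry-over does not reach. An equal shift of 0.10 in every epoch would move the planned contrast by 0.10 and the last-epoch model by 0.49 x 0.10 = 0.049.

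Fourth, collection ran from February to June 2024 and this version is dated March 1, 2025, so the change comes after collection. Dating it and keeping the planned model beside it answers this.

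**Conclusion.** The plan uses baseline only through subtraction of one epoch, and no RSA or IBI model adjusts for it. The consequence is a possible loss of precision of unknown size. With equal baseline and task variances the illustration gives about 2-22% on the SE, about 15% in the middle case. The loss can be close to zero if task variance is the larger, and is greater if task variance is the smaller. The reading of the plan is certain; the size rests on the assumed correlation, reliability, partner correlation and variances.

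A reader might infer three stronger things that the documents do not support:
- **That the planned test is biased or invalid.** Couples are randomized, and the change-score contrast is unbiased if baseline is unaffected by condition. The documents report no carry-over from threshold testing.
- **That the gain equals a definite number of extra couples, or that the stated power is wrong.** Any such conversion depends on unreported variances, and the power statement names no outcome.
- **That the five-minute mean should replace the last epoch.** Under settling it can do worse than the planned score.

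**What to change.** In the Statistical Analysis Plan's paragraph on physiological reactivity:
1. Keep the reactivity score as outcome. Add baseline RSA (or IBI) in the last 30 seconds as a fixed covariate to the condition model and to all follow-up models. The condition estimate is then the same whether the outcome is reactivity or segment level.
2. Report the planned no-covariate change-score model alongside.
3. As a sensitivity analysis, add the five-minute baseline mean as a second covariate. Do not use the mean alone.
4. Show baseline RSA and IBI by condition, for the last epoch and for the five-minute mean, because baseline follows randomization and threshold testing. The measures named in the randomization check include neither.
5. Date the change and state whether results by condition had been seen. If they had, label the adjusted model as additional.

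The cost is SAP wording, one extra fixed term in the main models, and scores for baseline epochs already recorded. No new data are needed and no participant is affected. The real cost is that the change is made after collection and must be disclosed as such.

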Clinical Trials Study Protocol

Examining Transcutaneous Vagal Nerve Stimulation as a Facilitator of Social Bonding (NCT05899413)

Version 1

March 1, 2025

This study was approved by the Institutional Review Board at the University of California, San Francisco (#23-39189). We conducted a power analysis prior to the data collection to determine the power for the Level-2 direct effect (stimulation condition) based on 1,000 simulations using the package *simr* in R (R Core Team). Given the nature of our dyad and the outcomes (i.e., questions about the same interaction), we assumed a large intraclass coefficient (0.5). Following Arend and Schäfer's (2019) recommendations, the standardized Level-1 direct effect was set to small ($\gamma_{std.} = .10$) in our power estimation for the Level-2 effect. Our analysis suggested that 70 dyads will provide > 82% power (α set to .05) to detect a medium-to-large standardized Level-2 direct effect ($\gamma_{std.} = .40$).

Data collection for the study took place between February and June 2024. Participants were recruited in the San Francisco Bay Area through various community and university newsletters and listservs, flyers around the city, Reddit, and word of mouth. We tried to reach diverse populations by promoting the study through various community centers (e.g., SF LGBT Center) and universities in the city (e.g., San Francisco State University, UC Berkeley).

Eligibility was confirmed using a screening questionnaire. Participants were eligible for the study if both they and their partner were between 18 and 35 years old, fluent in English, had no major chronic diseases (e.g., cardiovascular disease) or untreated psychiatric diagnoses, were not taking any confounding medications (e.g., antihypertensive medications), and did not have unremovable piercings on the tragus. We restricted the age range to control for age-related differences in physiological responses. As HRV tends to decrease with age, we attempted to recruit a more homogenous group on one of our primary outcome variables (HRV level and reactivity), so we capped the age range to mid-adulthood. Participants were also required to have been in a relationship with their partner for at least one year and be able to complete the inperson laboratory visit together.

Tasks and Measures

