Pre-visit survey. Prior to the lab visit, participants completed pre-visit surveys that collected information on basic sociodemographic characteristics, relationship characteristics, and physical attributes, including height and weight. Self-reported height and weight were used to compute Body Mass Index (BMI; weight (*lb*) ÷ height² (inches) * 703), which we used as a covariate. Participants also responded to a 5-item measure of relationship satisfaction (e.g., "I feel satisfied with our relationship"; $\alpha = .81$) and a 7-item measure of commitment (e.g., "I want our relationship to last for a very long time"; $\alpha = .79$) from the Investment Model Scale (Rusbult et al., 1988), which we used to test differences between participants in the experimental and control conditions. Additionally, they rated 24 relationship issues (e.g., communication, family and in-laws; adapted from Geiss & O'Leary, 1981) on a scale ranging from 0 (*issues that rarely if ever raise conflict or disagreement*) to 10 (*issues that raise frequent or intense conflict or disagreement*). Participants' responses to this scale were used in the conflict interaction described below.

Gratitude interaction. The procedures were based on Algoe and colleagues (2013). Couples were told to think about a positive thing their partner did for them recently for which they felt grateful. They were given three minutes to prepare, then took turns to express their gratitude for three minutes each. While one partner was speaking, the listening partner was told to listen with minimal verbal reactions.

Conflict interaction. The procedures were based on Levenson and Gottman (1983) and previous studies that examined physiological reactivity during conflicts (e.g., Godfrey & Babcock, 2020; Raby et al., 2015). Couples were told that they would discuss a conflict topic

relevant to their relationship and try to resolve it. The interaction would involve the following steps: 1) couples selecting a topic to discuss together, 2) reflecting on the topic independently for three minutes, 3) each partner taking turns expressing their thoughts and feelings about the topic for one minute (the speaking order was predetermined based on the alphabetical order of their first names), and 4) couples engaging in free discussion for six minutes, with the goal of resolving the issue.

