Notes. The time next to the lightning icon indicates the duration of the (active or sham) stimulation. The time at the bottom represents the duration of each study segment described within the rectangles. The survey icon indicates when participants complete short questionnaires.

Statistical Analysis Plan

All analyses will be conducted in R (R Core Team, 2022). Multilevel model analyses will be conducted using the packages *nlme* and *lmer*. All tests will be two-tailed, with a significance threshold of $\alpha = .05$.

Randomization check. We will first examine whether there are condition differences in personal and relational characteristics at baseline, including age, relationship duration, global relationship satisfaction, and commitment. To account for the interdependence of the dyadic data, we will fit a series of multilevel models with a random intercept included for participants nested within couples and condition included as a fixed effect. Restricted Maximum Likelihood will be used to fit the model parameters. For relationship duration, which is a couple-level variable, Welch's t-test will be conducted. **Study artifact check.** We will examine if there are condition differences in participants' experiences related to the stimulation and the tVNS device reported at the end of the study, including awareness of the stimulation, general discomfort, perceived influence of discomfort on interactions, and perceived influence of tVNS on interactions. We will run a parallel set of multilevel models as described above.

tVNS effects on emotional experience of the conflict. We will examine if there are condition differences in how couples self-report their experience of the conflict interaction, specifically in terms of positive and negative affect during the interaction. We will run a parallel set of multilevel models as described above.

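### If the nested intercept includes a couple level, the models cannot fit a negative partner covariance; should RSA or IBI reactivity show one, the condition test is conservative, and a free change removes this

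*Combined protocol and SAP*

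**What the plan says.** Couples, not individuals, are randomised, with equal chance of either arm (Study Procedure). Under Randomization check the SAP says: "we will fit a series of multilevel models with a random intercept included for participants nested within couples". Those models are fitted by REML, and the same form is reused for the stimulation-experience items and the affect ratings. Under tVNS effects on physiological reactivity it adds: "As in previously described multilevel models, we will include a random intercept for participants nested within couples", with autoregressive residuals. The named software is nlme and lmer.

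The only partner correlation in the documents is in the opening power paragraph: "Given the nature of our dyad and the outcomes (i.e., questions about the same interaction), we assumed a large intraclass coefficient (0.5". The plan does not say what happens if the couple variance is estimated as zero.

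**The concern.** Condition varies only between couples, so its standard error depends directly on how alike the partners are. A couple random intercept represents that likeness as a variance. If partners are less alike than two unrelated participants, the best available fit is a couple variance of zero, and the model treats the partners as independent. For a between-couple comparison that overstates the variance of the couple means.

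The reason given for 0.5 is that both partners answer questions about one interaction. That covers self-report. It does not carry over to RSA or IBI reactivity, where each person's own single 30-second baseline score is subtracted; noise in that score is person-specific and can pull the partner correlation toward zero. Nor does it clearly carry over to awareness and discomfort, because stimulation intensity is calibrated for each person separately. At stake are intervals that are too wide and tests that run below their nominal level. The risk is a missed effect, not a false positive.

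**Working it through.** **Inputs.** 70 couples, power above 82%, alpha .05: "70 dyads will provide > 82% power (α set to .05". Two-sided: "All tests will be two-tailed, with a significance threshold of" .05. Effect: "to detect a medium-to-large standardized Level-2 direct effect ($\gamma_{std.} = .40". Level-1 effect: "the standardized Level-1 direct effect was set to small ($\gamma_{std.} = .10". Partner correlation for planning: 0.5. Assumed: 35 couples per arm. The partner correlation r of participants' mean reactivity is not given, so a range is shown.

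**1. The plan's own power.** Take the effect as standardized on the couple-level SD, with condition as a unit-SD predictor (±1). The arms then differ by 2 × 0.40 = 0.80. Residual variances are 1 − 0.40² = 0.84 between couples and 1 − 0.10² = 0.99 within.
- Variance of a couple mean: 0.84 + 0.99/2 = 1.335.
- SE of the difference: √(2 × 1.335/35) = 0.276.
- Power: Φ(0.80/0.276 − 1.96) = 82.5% (81.5% with t on 68 df).

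This reproduces the stated figure. In participant SDs the effect is 0.80/√(0.84 + 0.99) = 0.59, and the implied partner correlation is 0.84/1.83 = 0.46.

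**2. Standard error under each covariance.** With participant variance 1, the true variance of the condition estimate is (4/70)(1 + r)/2. This gives an SE of 0.169 at r = 0 and 0.151 at r = −0.2. Let MSB and MSW be the between- and within-couple mean squares, on 68 and 70 df. A free partner covariance always uses MSB. A couple intercept uses MSB when MSB ≥ MSW, and otherwise the pooled value (68·MSB + 70·MSW)/138. At the boundary the SE is therefore too large by about 1/√(1 + r): at r = −0.2, 1/√0.8 = 1.12.

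**3. Results.** Simulation of MSB and MSW, at least 200,000 draws per cell, t on 68 df. Power is shown as couple intercept / free covariance.

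| r | Couple variance set to 0 | SE too large by | Type I error, couple intercept | Power at 0.59 SD | Power at 0.4 SD |
|---|---|---|---|---|---|
| 0 | 50% | 2.5% | 4.3% | 92.5 / 93.1% | 62.7 / 64.5% |
| −0.1 | 80% | 6% | 3.6% | 94.0 / 95.2% | 64.8 / 69.2% |
| −0.2 | 95% | 12% | 2.7% | 95.1 / 97.1% | 66.0 / 74.1% |
| −0.3 | 99% | 20% | 1.8% | 96.1 / 98.4% | 66.8 / 79.7% |

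The free covariance holds type I error at 5% throughout. At r = 0.3 or more the two models agree.

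**4. Repeated-measures check.** Six minutes of free discussion in 30-second epochs gives 12 segments. REML fits with couple and participant intercepts and AR(1) residuals (250 simulations per cell, r being the correlation of the participant intercepts) gave mean SEs, couple intercept against free, of 0.132 and 0.129 at r = 0, 0.129 and 0.117 at −0.2, and 0.129 and 0.110 at −0.3. The pattern is the same. The runs are too few to compare rejection rates.

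**5. The other reading of the intercept.** If only a participant intercept is fitted, the partner covariance is fixed at zero. Negative values are still excluded, but positive ones now make the SE too small: type I error is 8.4% at r = 0.3 and 10.8% at r = 0.5.

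**The case against.** The strongest objection is that nothing in the documents makes a negative correlation likely. The one figure given is +0.5, and partners share the room, the topic and the condition, all of which push toward likeness. A dyad random intercept is an ordinary choice, and its error here is on the safe side. All of this stands, and it limits the point to a low-priority improvement.

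Four stronger readings are tempting and are not supported:

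- **That partners' reactivity must move in opposite directions because they compete for talk time.** The documents neither report talk time in the free discussion nor link speaking to RSA. The structured phase has "each partner taking turns expressing their thoughts and feelings about the topic for one minute". Both partners therefore fill both roles for equal time, which gives no reason for a negative correlation of their means.
- **That the trial falls short of its stated power.** For a fixed effect in participant SDs, power under the couple intercept rises as r falls, because the true variance of the couple means shrinks. At 0.59 SD it is 92.5% or more for r at or below 0. The loss is relative to the better model, not to the plan.
- **That the point is the same however the nested intercept is read.** Step 5 shows otherwise. With a participant intercept alone, the larger problem would be inflated type I error at positive correlations. The couple-level reading is the more natural one, because with a single rating per person a participant intercept cannot be separated from the residual, but the SAP should say so.
- **That the artifact check will hide an arm difference.** Individual calibration suggests at most a correlation near zero, where the SE is about 2.5% too large.

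**Conclusion.** The point holds as a conditional, minor one. It rests on three assumptions: a couple-level intercept is fitted, 70 couples split 35 and 35, and a partner correlation that the documents do not give. If that correlation is near zero, the cost is small: 0.6 points of power at the planned effect and just under 2 points at 0.4 SD. It grows at −0.1 and below, reaching about 2 points at 0.59 SD and 13 points at 0.4 SD when the correlation is −0.3. If the correlation is clearly positive, there is no cost. For the affect ratings, if their correlation is near the assumed 0.5, nothing changes. No result would be falsely positive because of the bound. The case for acting is that the better covariance costs nothing in sample size or parameters and also settles the ambiguity over which intercepts are meant.

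**What to change.** Before the unblinded analysis, specify a compound-symmetric partner covariance that may be negative, and use it whatever sign is estimated.

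- **RSA and IBI:** in nlme, replace the nested intercepts with `random = list(couple = pdCompSymm(~ 0 + partner))` and `corAR1(form = ~ epoch | couple/partner)`, with partner as a two-level factor. This keeps AR(1) residuals within participant.
- **Single-rating outcomes** (baseline characteristics measured per person, stimulation experience, affect): `gls` with `corCompSymm(form = ~ 1 | couple)`.
- **Degrees of freedom:** test condition on couples minus 2 (70 − 2 = 68) in both. For `gls` this must be set explicitly, because its default is observations minus parameters (140 − 2 = 138 with condition alone).

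If the analyses have already been run, report this as a sensitivity analysis beside them; a comparison of couple means is a simple further check.

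The cost is a short SAP edit, two model calls and the manual degrees of freedom. It needs no new data and adds no covariance parameter, since one partner covariance replaces one couple variance. It also gives valid standard errors where a participant-only intercept would not.
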